11.2 Sample size calculation

A formal sample size calculation was not possible for this study therefore a realistic number of participants has been selected based on previous experience of similar research studies by [name], [name] and [name].

Brodie FG et al reported in 2009 that a sample of 11 patients per group will allow the detection of a difference in ARI of 2 units between groups, with 80% power at the 5% significance level.

11.3 The Level of Statistical Significance

Statistical significance will be set at $p < 0.05$

11.4 Procedure for Accounting for Missing and Unused Data

Unused data will be reported, with reasons in the final report after study completion, and in any publication. Spurious and missing data will be reported, but not included in final analyses.

12. DIRECT ACCESS TO SOURCE DATA/DOCUMENTS

Direct access will be granted to authorised representatives from the Sponsor, host institution and the regulatory authorities to permit trial-related monitoring, audits and inspections.

13. QUALITY CONTROL AND QUALITY ASSURANCE PROCEDURES

The study will be conducted in accordance with the current approved protocol, ICH GCP, relevant regulations and standard operating procedures.

The University of Leicester operate a risk based monitoring and audit programme to which this study will be subject.

14. CODES OF PRACTICE AND REGULATIONS

14.1 Ethics

All informed consent taken from TIA patients and HC subjects will be taken following GCP guidelines.

14.2 Sponsor Standard Operating Procedures

All relevant Sponsor SOPs will be followed to ensure that this study complies with all relevant legislation and guidelines.

14.3 Declaration of Helsinki

The Investigator will ensure that this study is conducted in full conformity with the current revision of the Declaration of Helsinki (last amended October 2000, with additional footnotes added 2002 and 2004).

14.4 ICH Guidelines for Good Clinical Practice

The Investigator will ensure that this study is conducted in full conformity with relevant regulations and with the ICH Guidelines for Good Clinical Practice (CPMP/ICH/135/95) July 1996.

14.5 Approvals

Once Sponsor authorisation has been confirmed, the protocol, informed consent form, participant information sheet and any proposed advertising material will be submitted to an appropriate Research Ethics Committee (REC), Health Research Authority (HRA), and host institution(s) for written approval.

Once Sponsor authorisation has been confirmed, the Investigator will submit and, where necessary, obtain approval from the above parties for all substantial and non-substantial amendments to the original approved documents.

14.6 Participant Confidentiality

The trial staff will ensure that the participants' anonymity is maintained. The participants will be identified only by initials and a participants ID number on the CRF and any electronic database. All documents will be stored securely and only accessible by trial staff and authorised personnel. The

study will comply with the Data Protection Act which requires data to be anonymised as soon as it is practical to do so.

15. DATA HANDLING AND RECORD KEEPING

15.1 Data Extraction

As supportive evidence of the diagnosis of TIA in TIA participants, results and significant findings from Computerised Tomography (CT) head/Brain Magnetic Resonance Imaging (MRI) and Carotid Ultrasound, if undertaken, will be recorded on the CRF.

Other information which will be extracted from the medical notes of TIA participants and recorded on the CRF include smoking status, capillary blood glucose, medications, past medical history, height, weight and BMI.

The medical notes of healthy control participants will not be reviewed, and participants will instead be asked their smoking status, medications, past medical history, height and weight directly. Answers to these questions will be recorded on the CRF.

Data regarding participants' age, date of birth, ethnicity and handedness will also be recorded onto the CRF. All other parameters, including CBFv, squat angle, heart rate (HR), BP, and ETCO₂, will be recorded onto a computer system (PHYSIDAS), providing data for subsequent analyses.

15.2 Data Analysis

Off-line analyses will be undertaken using software designed by the University of Leicester's Medical Physics Group.

15.3 Data Management

Baseline and demographic data will be recorded on the CRF, which will be retained in the study site file. This will be stored within a locked filing cabinet, within a locked office in a building which requires swipe card or security review for access at the University of Leicester. CRF data will be anonymised for storage on a secure drive on encrypted, password protected, university desktop computers.

Personal data that cannot be anonymised (e.g. contact details and enrolment logs) will be stored within a locked filing cabinet, within a locked office in a building which requires swipe card or security review for access at the University of Leicester and/or within a password protected file, on an encrypted, password protected, desktop computer which is kept within a locked office. No personal data will be accessed or stored on personal laptops.

CONFIDENTIAL

All physiological parameters (signals) that are collected during the measurement will be saved using a coded filename. The participant name and other identifying detail will NOT be included in any study data electronic file. All study data will be entered into Microsoft Excel for Windows on an encrypted, password protected, desktop computer which is kept within a locked office. .

Anonymised outcome data will be held on an encrypted, password protected desktop computer which is kept within a locked office. Anonymised outcome data may also be held on an encrypted, password protected personal laptop belonging to researchers named on the authorisation log.

Participants will be identified by a study specific participants number and/or code in any database. Names and any other identifying detail will NOT be included in any study data electronic file.

Anonymised research data may be shared with researchers from other Departments or Universities conducting similar research. Information regarding this will be detailed in the PIS, and explicit written consent for the sharing of such data will be obtained from participants.

16. STUDY GOVERNANCE

The trial management group, which consists of the CI, co-investigators, and other research staff, will meet monthly to monitor study progress, and recruitment targets. As this is a prospective case control study, and not a therapeutic study, a data safety monitoring committee is not required.

17. FINANCING AND INSURANCE

In this study [name] and [name] will supervise the researcher who is responsible for participant recruitment, data collection and analysis. [name] will take a lead role in preparing the experimental procedures and then guiding participant recruitment. [name] will supervise data analysis and will also have a key role in the interpretation of results.

In this study, the assessments on participants will be carried out by the researcher, and all the equipment to be used is provided, serviced and maintained by the Department of Medical Physics, University of Leicester.

There are no NHS treatment or support costs.

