6.2 Primary and Secondary Endpoints/Outcome Measures

This is not an intervention study, and therefore it would not be appropriate to assess classical primary and secondary outcome measures such as death and disability for this study. However, we intend to evaluate the following relevant outcomes:

- a) The number of participants recruited
- b) The number of participants able to comply with the full measurement protocol
- c) The number of measurements rejected because of aspects related to data quality during the analysis protocol, with recorded reasons
- d) Overall, the number of recruited subjects in whom values for the following parameters can be derived:
 - % change of cerebral blood flow velocity (CBFv) at baseline in response to performance of a squat-stand manoeuvre
 - Autoregulation index

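### Data rejection at the analysis stage has no stated criterion and no stated masking of TIA/HC status, so it could bias the group comparison

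*Combined protocol and SAP*

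**What the plan says.** Section 17 describes the staffing. Senior investigators "will supervise the researcher who is responsible for participant recruitment, data collection and analysis", and "the assessments on participants will be carried out by the researcher". A senior role "will supervise data analysis and will also have a key role in the interpretation of results"; this is not described as masked or as an independent second reading.

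Section 6.2 lists as an outcome "The number of measurements rejected because of aspects related to data quality during the analysis protocol, with recorded reasons", which places rejection at the analysis stage. Section 11.4 states "Spurious and missing data will be reported, but not included in final analyses" and adds "Unused data will be reported, with reasons in the final report after study completion, and in any publication". Neither section defines spurious or gives a threshold for artefact, coherence or signal quality. On method, section 15.2 says only "Off-line analyses will be undertaken using software designed by" the university's medical physics group.

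The nearest thing to masking is in section 15.3: "All physiological parameters (signals) that are collected during the measurement will be saved using a coded filename". It stands among the data-protection provisions. It does not say that the code hides group or that the analyst lacks the key.

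Section 11.1 makes the TIA versus HC comparison of CBFv and ARI one of the null hypotheses to be tested.

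**The concern.** Read together, these sections let one person meet each participant, learn the group, make the recording and later decide which recordings count. If judgements about quality are influenced by knowing the group, and those judgements are related to the value that a recording yields, the two groups are trimmed differently. A difference in ARI or CBFv could then appear, or be hidden, for reasons unrelated to autoregulation.

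The setting leaves room for judgement. Section 8.5 lets participants choose their squat depth and stop early, so recording quality may vary. Section 4 itself notes that low coherence often leads to data being left out of such analyses. With 20 per group, a few lost participants can move a mean. Two of the feasibility outcomes in section 6.2, the number of measurements rejected and the number of participants with derivable values, also depend on a criterion that is not written down.

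**Working it through.** **Step 1: does any passage mask or standardise rejection?**

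| Question | Where | What is stated |
|---|---|---|
| Who measures and analyses? | 17 | The same researcher, supervised |
| When are data rejected? | 6.2 | During analysis |
| By what rule? | 11.4, 15.2 | None given |
| Is group hidden? | 15.3 | Coded filename; group not mentioned |
| Is there a second, masked reader? | 17 | Not stated |

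Two links are inferences. That this researcher makes the rejections follows from responsibility for analysis (17) plus rejection during analysis (6.2). That the work is unmasked follows from silence, not from a declaration.

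**Step 2: an SD for illustration.** The documents give none. Section 11.2 cites 11 per group to detect 2 ARI units with 80% power at the 5% level. Without an SD that figure cannot be reproduced, but it can be solved backwards, taking the test as two-sided (an assumption):

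- Normal approximation: SD = 2 / [√(2/11) × (1.960 + 0.842)] = 1.67.
- Noncentral t: SD = 1.59, used below.

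**Step 3: expected spurious shift.** Assume no true difference, 20 per group, and two whole participants rejected per group: those who look highest in TIA and lowest in HC, on an impression that has correlation r with ARI. The expected highest and second-highest of 20 standard normal values are about 1.87 and 1.41.

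- Shift in one group: r × (1.87 + 1.41)/18 = 0.182 r SDs.
- Both groups, opposite directions: 0.364 r SDs.
- At SD 1.59: 0.58 r ARI units.

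**Step 4: false-positive rate.** Simulated null trials, two-sided t-test at 0.05. The t-test stands in for the between-group part of the planned ANOVA.

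| r (assumed) | Shift, ARI units | False-positive rate, two per group |
|---|---|---|
| 0 | 0 | about 5% |
| 0.3 | 0.17 | about 6% |
| 0.5 | 0.29 | about 9% |
| 1 | 0.58 | about 26% |

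**Step 5: sensitivity of the illustration.**

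- Two rejected in TIA only, r = 1: about 10%, shift 0.29. This is the ceiling for that pattern.
- One rejected per group, r = 1: about 11%.
- Four in TIA and none in HC, r = 0: 5%. Unequal rejection counts alone do no harm in this setting.
- Four per group, r = 1: about 63%. The number that will be rejected is not given in the documents.
- SD 1.0 to 2.0, two per group, r = 1: the rate stays near 26%; the shift runs from 0.36 to 0.73.

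**Step 6: with group-blind rejection.** Removing the two or four highest of the pooled 40 values regardless of group gives a shift of about 0 and a false-positive rate of about 5% (SD 1.6).

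**The case against.** The strongest reply is that the documents do not show unmasked rejection at all. No passage names who rejects, a senior role supervises the analysis, the in-house software may handle artefacts in a way that is not described, and the files are coded. A reader might infer that the plan declares an open, unmasked edit by one person. The documents do not support that; they are silent. What remains is that nothing in them prevents it, and a filename code gives no assured masking when the person reading the file made the recording.

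Second, the large figures describe deletion by outcome value, in opposite directions, without error, whereas section 6.2 speaks of rejection for data quality. This stands. A reader might take 11% or 26% as the expected error rate; those figures belong to the extreme case, and a quality judgement unrelated to ARI leaves the test at 5%.

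Third, the unit is too coarse. Each participant gives bilateral signals and up to 15 squats (8.5), section 4 cites evidence that three manoeuvres can suffice, and inadequate windows are screened out first (8.3). Losing a segment or one side need not lose a participant. This also stands and points to smaller effects.

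Fourth, reasons for rejection are recorded and published. That makes selective rejection visible afterwards, but does not prevent it.

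**Conclusion.** The point holds as a weakness in the plan: rejection is neither criterion-based nor stated to be masked, while the one researcher's role covers recruitment, measurement and analysis. Rejection could therefore bias the TIA versus HC comparison. The documents do not show that it will, and they give neither its direction nor its size.

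Under the stated assumptions (no true difference, two whole participants lost per group in opposite directions), the false-positive rate lies between about 5% and 26%, with 6% to 9% at correlations of 0.3 to 0.5. The spurious shift is 0 to 0.58 ARI units; even its upper end is under a third of the 2 units cited in section 11.2 (0.58/2 = 0.29). The SD, the correlations and the number rejected are all assumptions. This is a cheap improvement, and confidence is medium because two links in the argument are inferred.

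**What to change.** Amend sections 11.4 and 15.3 as follows.

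1. Before off-line analysis, an existing co-investigator or supervisor re-labels the signal files with random codes that carry no group information, and holds the key.
2. The researcher edits, accepts or rejects, and derives CBFv and ARI on these files, using written signal-quality criteria fixed beforehand.
3. The accept/reject log is locked before the key is opened.
4. Rejections are reported by group, with reasons.

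A repeat of the comparison that includes rejected recordings from which a value can still be derived is useful as a sensitivity analysis only. It brings back data that section 11.4 excludes, so it should not replace the main result.

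The cost is a short delay and the work of writing the criteria, which is the larger task. No extra participants, visits or staff are needed. Masking will be imperfect because the same researcher made the recordings and may recognise some of them; the fixed criteria limit the damage when that happens.

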18. PUBLICATION POLICY

On all publications, the host institution will be acknowledged, and each author will be required to disclose details of their own involvement/contribution in the study (specific publication).

20. APPENDIX A: CATEGORISATION OF ETHNICITY

White

1. English / Welsh / Scottish / Northern Irish / British
2. Irish
3. Gypsy or Irish Traveller
4. Any other White background, please describe

Mixed / Multiple ethnic groups

5. White and Black Caribbean
6. White and Black African
7. White and Asian
8. Any other Mixed / Multiple ethnic background, please describe

Asian / Asian British

9. Indian
10. Pakistani
11. Bangladeshi
12. Chinese
13. Any other Asian background, please describe

Black / African / Caribbean / Black British

14. African
15. Caribbean
16. Any other Black / African / Caribbean background, please describe

Other ethnic group

17. Arab
18. Any other ethnic group, please describe

21. APPENDIX B: EDINBURGH HANDEDNESS INVENTORY

Please indicate with a check (✓) your preference in using your left or right hand in the following tasks.

Where the preference is so strong you would never use the other hand, unless absolutely forced to, put two checks (✓✓).

If you are indifferent, put one check in each column (✓ | ✓).

Some of the activities require both hands. In these cases, the part of the task or object for which hand preference is wanted is indicated in parentheses.

Task / Object	Left Hand	Right Hand
1. Writing		
2. Drawing		
3. Throwing		
4. Scissors		
5. Toothbrush		
6. Knife (without fork)		
7. Spoon		
8. Broom (upper hand)		
9. Striking a Match (match)		
10. Opening a Box (lid)		
Total checks:	LH =	RH =
Cumulative Total	CT = LH + RH =	
Difference	D = RH – LH =	
Result	R = (D / CT) × 100 =	
Interpretation: (Left Handed: R < -40) (Ambidextrous: -40 ≤ R ≤ +40) (Right Handed: R > +40)		

22. APPENDIX C: SCHEDULE OF PROCEDURES

PROCEDURES	VISIT	
	Screening	Baseline
Informed consent	0	1
Demographics	1	1
Medical history	1	1
Concomitant medications	1	1
Eligibility assessment	1	0
Ethnicity categorisation	0	1
Handedness	0	1
Cerebral Haemodynamic Assessment (TCD, blood pressure, ECG, ETCO ₂)	0	1

23. APPENDIX D: EXPECTED EVENTS NOT SUBJECT TO EXPEDITED REPORTING

Acute Coronary Syndromes	Malignancy
Agitation	Myocardial infarction
Angina	Nausea
Anorexia	Personality change
Anxiety	Peripheral Vascular Disease
Cognitive decline	Pressure sores
Constipation	Renal impairment
Delirium	Sedation
Depression	Seizure
Disease progression	Sexual dysfunction
Dysphagia	Sleep disturbance
Electrolyte disturbance	Stroke
Fall	Syncope
Fatigue	Transient ischemic attack
Fracture	Urinary retention/catheterisation
Gastrointestinal disturbance	Urinary tract infection
Hallucinations	Ulceration
Heart failure	Violent behaviour
Incontinence, faecal	Visual loss
Incontinence, urinary	Vomiting
Infections	Wandering
Institutionalisation / Admission to care home	Weakness
Intracerebral Haemorrhage	Weight loss
Loss of ability to function or care for self
